## **STUDY PROTOCOL.**

### **HYPOTHESIS**

Steroids form one of the pillars of immunosuppression in transplant patients. However, their use is associated with an increase in post-transplant comorbidity. Although steroid withdrawal post-transplant can improve the metabolic and cardiovascular profile in transplant patients, it is not really known whether this therapeutic strategy results in a greater risk for the de novo appearance of donor-specific antibodies (DSA), which are associated with a reduction in kidney graft survival. Also unknown is the causal relationship between the appearance of DSA and histological lesions in stable kidney transplant patients after steroid withdrawal in the third post-transplant month. Finally, another unknown is whether this immunosuppressive strategy is associated with changes in the balance between effector and suppressor lymphocyte subpopulations that selectively infiltrate the graft via peripheral homing receptors.

This randomized controlled study of stable kidney transplant patients aimed to determine the natural history after steroid withdrawal in the third month post-transplant of the de novo production of anti-HLA antibodies (DSA), by means of the sequential measurement of DSA during the first two years post-transplant. At the same time we wished to determine the repercussion of this therapeutic strategy on the kidney graft histology by performing protocol biopsies, as well as the risk factors for the appearance of de novo DSA in these patients. Finally, we aimed to monitor sequentially the balance of the lymphocyte (CXCR3highCD4+/CCR4highCD4+) and regulatory cell (Treg CCR4high) subpopulations in peripheral blood and samples of the graft tissue obtained by fine-needle aspiration puncture (FNAP) after the withdrawal of steroids versus continuation of conventional triple therapy.

The lack of prospective serological, histological and lymphocyte subset studies in kidney transplant patients in whom steroids are withdrawn makes this study very pertinent. The findings will doubtless give rise to an immunosuppressive strategy that optimizes the results of a transplant in terms of survival.

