### *Secondary objectives*

1. To determine the course of the histological findings in the two treatment groups.
2. To determine the course of the balance in the subpopulations of lymphocytes (CXCR3highCD4+/CCR4highCD4+) and regulatory cells (Treg CCR4high) using flow cytometry in samples from peripheral blood and FNAP after withdrawal of steroids in the third month post-transplant versus conventional triple immunosuppression.
3. To analyze and compare the incidence of immunological dysfunction in the two treatment arms, as well as graft and patient survival at one and two years of follow-up.
4. To examine the potential metabolic and cardiovascular benefit of steroid withdrawal in terms of renal function, hypertension, diabetes and hyperlipidemia.
5. To assess the adherence to treatment with immunosuppressors in the two treatment groups and its impact on the generation of DSA.

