### **Variables:**

#### *Efficacy variables:*

The *primary variable* was the presence of donor-specific anti-HLA antibodies (DSA) at 24 months.

The *secondary variables* were:

- a) Graft and patient survival.
- b) Rate of acute clinical rejection, confirmed by biopsy, calculated glomerular filtration rate (determined by aMDRD) and proteinuria at 3, 6, 12 and 24 months.
- c) BP figures and number of hypertensive patients, lipid levels and need for lipid-lowering drugs, and increase in weight and BMI.
- d) Rate of post-transplant diabetes mellitus (PTDM) or glucose intolerance one year post-transplant according to the criteria of the ADA (PTDM: baseline glycemia  $\geq 126$ , or  $\geq 200$  mg/dl after glucose overload, or need for treatment; glucose intolerance: glycemia after overload of 140-199 mg/dL).
- e) Determination of the lymphocyte subpopulations (CXCR3highCD4+; CCR4highCD4+ and Treg CCR4high) by flow cytometry at 1, 3, 6, 12, 18 and 24 months.
- f) Appearance of acute or chronic pathological lesions of the graft using:

\*Kidney graft biopsy. Biopsies were done before randomization (month 3 post-transplant) and in month 24 post-randomization (protocol biopsies). In the case of suspected acute rejection a biopsy of the graft was done before or within 48 hours of starting anti-rejection treatment. Likewise, a graft biopsy was done at any time if graft dysfunction was detected, as evidenced by proteinuria 0.5 g/day or an increase in the serum creatinine of 25% above its baseline level. The biopsies were evaluated according to the Banff'09 classification (*Sis B, et al Am J Transplant 2010;10: 464-71*). Biopsies done for clinical indication and those done prior to randomization were evaluated locally at each participating center. The local pathologist interpreted the biopsy for the presence of clinical or subclinical rejection, borderline lesions or progression of chronic lesions that

explained a possible graft failure to thus provide the most opportune treatment. The biopsies done and the pre-randomization and final visits were also sent to the pathologist at Carlos Haya Hospital, Malaga, who also interpreted and classified them using the same Banff'09 criteria. The biopsies were processed in each center and sent to the central pathologist for study. The slides comprised at least 2-3 slices of the biopsy. The staining was done locally (hematoxylin eosin, periodic acid Schiff, Masson trichrome and methenamine silver).

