## **STATISTICAL ANALYSIS PLAN.**

Descriptive statistics are presented together with the various analyses. Both an intention-to-treat analysis and an analysis according to the final treatment were done. The categorical variables were analyzed using the chi-square test or Fisher's exact test, according to needs. The quantitative data were analyzed using the Student t test or the Mann-Whitney U test, according to needs. Changes over time in the DSA and lymphocyte subsets in the two study groups were analyzed using a general linear model for repeated measures, adjusting for confounding variables. Correlations between the various subsets were analyzed using Pearson correlation. The graft and patient survival curves were calculated with the Kaplan-Meier method. The rates of survival of the groups were compared with the log-rank test. Finally, a linear regression analysis was done to determine the factors associated with the generation of de novo DSA, including steroid withdrawal. The data were analyzed using SPSS 20.0.

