### **Lymphocyte subpopulations.**

A significant increase was seen in lymphocyte subpopulations in the FNAP samples compared to the peripheral venous blood samples. Likewise, the patients with borderline lesions showed an

increase in the CXCR3highCD4+ and CD14+CD16+ subpopulations in venous blood and FNAP samples compared to the patients with no subclinical inflammation in the biopsy.

Additionally, a direct correlation was found between the CD14+CD16+ subset obtained by FNAP at 3 months and the presence of IFTA at 24 months. Likewise, the CCR4highCD4+ lymphocyte subset obtained at 3 months post-transplant correlated inversely with the interstitial ( $r=-0.431$ ;  $P=0.007$ ) and tubular ( $r=-0.436$ ;  $P=0.007$ ) inflammation at 24 months post-transplant.

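### Secondary objective 2 asks whether steroid withdrawal shifts the effector/regulatory balance, but no balance measure is defined and the preliminary results report no comparison by arm

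*Combined protocol and SAP*

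**What the plan says.** The Hypothesis section asks whether withdrawal is "associated with changes in the balance between effector and suppressor lymphocyte subpopulations", to be monitored in blood and graft aspirate "after the withdrawal of steroids versus continuation of conventional triple therapy". Item 2 of Secondary objectives begins "To determine the course of the balance in the subpopulations of lymphocytes (CXCR3highCD4+/CCR4highCD4+) and regulatory cells (Treg CCR4high" and names the same contrast: "after withdrawal of steroids in the third month post-transplant versus conventional triple immunosuppression". The question therefore has two parts: a balance, and a comparison of arms.

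Under Efficacy variables, secondary variable (e) is "Determination of the lymphocyte subpopulations (CXCR3highCD4+; CCR4highCD4+ and Treg CCR4high) by flow cytometry", measured at six visits from month 1 to month 24. The three subsets are separate items.

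The Statistical Analysis Plan applies a general linear model for repeated measures to the lymphocyte subsets in the two groups, adjusted for confounders. It adds: "Correlations between the various subsets were analyzed using Pearson correlation".

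The Lymphocyte subpopulations part of the Preliminary Results opens with "A significant increase was seen in lymphocyte subpopulations in the FNAP samples compared to the peripheral venous blood samples". It goes on to patients with and without borderline lesions, and to correlations between month-3 subsets and month-24 histology.

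**The concern.** A balance is a relation between two subsets within one patient. Tests on each subset separately do not settle it. If both rise by the same proportion, each test may be positive while the balance is unchanged. If they move a little in opposite directions, each test may be negative while the balance has moved. A correlation between subsets shows whether they vary together across patients, which is neither a patient's balance nor a treatment contrast.

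The second gap is in reporting. The only lymphocyte findings shown compare tissue compartments or histological groups, and those comparisons are not protected by randomisation. A reader could take them as evidence on withdrawal, which they are not. At stake is one named secondary objective and one part of the hypothesis. The primary result on donor-specific antibodies is unaffected.

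**Working it through.** The documents state no sample size, power, SD or effect size for this outcome, so there is no design figure to reproduce. The main check compares the texts.

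1. **Is a balance variable defined?** The objective writes the first pair with a slash, CXCR3highCD4+/CCR4highCD4+. Variable (e) separates the same two with a semicolon. The flow cytometry and FNAP sections describe how the subsets are measured, and the analysis plan derives nothing from them. Elsewhere the protocol does define composites where it wants them: the corrected index for FNAP and the summed chronic lesion score. None exists for objective 2.

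2. **Is an arm comparison planned?** Yes, for the subsets, through the repeated-measures model.

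3. **Is an arm comparison reported?** No. The contrasts shown are FNAP versus blood, borderline lesions versus no inflammation, and correlations with month-24 lesions. Treg CCR4high does not appear. CD14+CD16+ does appear, although it is in neither objective 2, variable (e) nor the listed antibody panel. The correlated subsets were taken at month 3, the time of randomisation, so they cannot show an effect of later withdrawal. By contrast, diabetes, lipids, blood pressure, renal function and serious adverse events are all reported by group with p-values.

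4. **How many patients lie behind the correlations?** Assume Pearson correlations with the usual test, t = r√((n−2)/(1−r²)). For r = −0.431, n = 38 gives P = 0.0069. For r = −0.436, n = 37 gives P = 0.0070. Both round to the reported 0.007, and neighbouring values of n do not. The correlations therefore rest on about 37 or 38 patients, against 105 randomised.

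5. **What would a ratio do to power? (Illustration only.)** Assumptions: log-scale subsets each with SD 1, between-subset correlation ρ, 52 and 53 patients with complete data, one time point, two-sided 5% t test with 103 df. The log ratio has SD √(2(1−ρ)). Non-centrality is d·√(52·53/105) = 5.123·d. For one subset with d = 0.3 this is 1.54, giving 33% power. For the log ratio, d = 0.6/√(2(1−ρ)) if the subsets shift 0.3 SD in opposite directions, and d = 0.3/√(2(1−ρ)) if only one shifts.

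| ρ | SD of log ratio | Power, opposite shifts | Power, one subset shifts |
|---|---|---|---|
| −0.3 | 1.612 | 47% | 16% |
| 0 | 1.414 | 58% | 19% |
| 0.3 | 1.183 | 73% | 25% |
| 0.5 | 1.000 | 86% | 33% |

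If both subsets shift equally in the same direction, the log ratio does not change at all. If only about 38 patients had data (assumed 19 per arm), power would be 15% for one subset and 20% to 44% for the ratio under opposite shifts.

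**The case against.** Four points can be made for the plan.

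First, a reader might infer that no randomised comparison of lymphocytes was planned. That is wrong: the analysis plan models the subsets in the two study groups with adjustment. The arm comparison is planned but unreported. This stands and narrows the point.

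Second, a reader might infer that the comparison was never made. The results are a short section labelled preliminary, so absence there does not show absence of analysis. This also stands: the question is unanswered in this document, and no more can be said.

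Third, the slash in the objective can be read as a ratio. That is fair as a hint, but it never becomes an endpoint with a scale, a compartment or a time point. A ratio of effector cells to Treg CCR4high is not written as a pair anywhere.

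Fourth, a reader might infer from the opposite-shift column that a ratio is worth 2/(1−ρ), or 1.5 to 4, times the sample size for free. That holds only in the case most favourable to it. If one subset alone shifts, the factor is 1/(2(1−ρ)), or 0.38 to 1.0. The documents give no SD, effect or correlation with which to choose between these cases, so the argument does not rest on power.

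**Conclusion.** The point holds in a limited form. Objective 2 is a between-arm question about a balance. The outcome and the analysis plan contain no measure of balance, and the preliminary results contain neither an arm comparison for any lymphocyte subset nor any Treg CCR4high result. This rests on the text alone. The power figures are illustrations under the stated assumptions and favour neither approach in general. The matter is worth correcting because a stated objective is left open and associations not split by arm occupy its place. It concerns a secondary, mechanistic objective only.

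**What to change.** - Derive log(CXCR3highCD4+/CCR4highCD4+), the pair written in objective 2, separately in blood and in FNAP. Add a log ratio of effector cells to Treg CCR4high as supportive.
- Name one main time point, for example month 24 to match the primary variable. Otherwise two ratios, two compartments and four post-randomisation visits (months 6, 12, 18 and 24) give 2 × 2 × 4 = 16 contrasts.
- State a rule for zero counts, which are plausible for a small sub-gate in roughly 20 µL of aspirate.
- Run the planned repeated-measures model by randomised group on the ratios and on every single subset, including Treg CCR4high. Report arm differences with 95% confidence intervals and the number of patients per arm, ahead of the associations.
- Label the ratios post hoc, because results already exist, and label the associations exploratory.
- If this is not done, state that objective 2 was not assessed.

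The cost is derived variables from measurements the protocol already specifies, one set of model runs, and wording. The downside is that a ratio has at most the power of a single subset when only that subset shifts, at correlations up to 0.5 in the illustration. That is why the single-subset comparisons stay.

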## STUDY DESIGN AND DURATION

This was a randomized, open-label clinical trial with two treatment arms and a follow-up of two years in patients who received a first deceased-donor kidney transplant. The combinations of immunosuppressors in the study arms were those approved in the technical documentation and used routinely in clinical practice. This was therefore a phase IV clinical trial in the usual conditions of use. The patient recruitment period was 12 months. The minimum follow-up period was 24 months.

**Inclusion criteria:** a) Both male and female patients, 18 years of age or over with no immunological risk (PRA <25% and absence of DSA) who received a first deceased or living donor kidney transplant. b) Patients who for the first three months post-transplant were receiving tacrolimus plus MPA or MMF and steroids and who had stable plasma levels of tacrolimus. c) Absence of clinical or histological immune dysfunction before randomization. d) Absence of de novo DSA at the time of randomization. e) Patients who wished and were able to give their written informed consent to participate in the study. f) Female patients who agreed to use efficient contraceptive methods during the study.

**Exclusion criteria:** a) Recipients of a multiorgan transplant. b) Retransplants. c) Presence of DSA prior to transplant or at the time of randomization. d) Cold ischemia time >30 hours. e) Patients with serum creatinine levels above 2 mg/dL or proteinuria above 1g/day at the time of randomization. f) Previous episode of severe rejection (II-B-III in the Banff/09 classification) before randomization. g) Presence of subclinical rejection in the protocol biopsy before randomization. h) Patients with BK-polyomavirus nephropathy at the time of randomization. i) Patients with recurrent or de novo glomerulonephritis. j) Patients receiving treatment with immunosuppressive drugs other than those of the clinical trial in question. k) Patients who were positive against the human immunodeficiency virus (HIV) or who had a severe systemic infection and who the investigator deems the need for continued therapy. l) Patients who had had any previous malignant disease during the previous five years, except basal cell or excised squamous cell carcinoma.

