**Selection procedure and coding:** Once written informed consent was obtained at the screening visit, the baseline data were collected to determine the eligibility of the patients to participate in the study. Those patients who fulfilled the inclusion criteria were randomized in a proportion 1:1 to one of the two treatment arms.

Randomization was done locally at each center via the case report form (CRF) to assign the eligible patients to one of the two treatment arms. This randomization was done using a computer program after introducing the patient data into the electronic database (CRF) and determining the

status of the anti-HLA antibodies (DSA) and the histological findings at the third month post-transplant.

**Description of the treatment groups:** After verifying the inclusion/exclusion criteria, the patients were distributed randomly in the two study groups:

**Group A:** steroids, tacrolimus (prolonged-release –Advagraf, or immediate-release tacrolimus – generic or Prograf, according to their availability in each Community) plus MMF or MPA.

**Group B:** tacrolimus (prolonged-release –Advagraf, or immediate-release tacrolimus –generic or Prograf, according to their availability in each Community) plus MMF or MPA.

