For the measurement of C4d an unstained slide was sent to the reference center, at ambient temperature.

\*The interpretation of the central pathologist was used mainly to analyze the progression of the chronic graft nephropathy. For each patient, the sum of the classification of the chronic lesion was obtained from the 5 histological categories: 1) cg: chronic glomerulopathy. 2) ci: chronic interstitial. 3) ct: tubular atrophy (chronic). 4) cv: arteriolar hyalinosis (chronic). 5) mm: mesangial matrix.

*Confounding variables:* Donor and recipient age, HLA compatibility and PRA, delayed graft function, BMI, CMV infection, concomitant treatment (statins, ACEIs/ARA, beta blockers, diuretics, and ASA), scale of treatment compliance and levels of tacrolimus or CsA.

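### Biopsy-confirmed rejection, a secondary outcome of an open-label trial, rests on local readings, and the plan states neither whether readers were masked nor which reading defines an event.

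*Combined protocol and SAP*

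**What the plan says.** Study design and duration describes the trial in these terms: "This was a randomized, open-label clinical trial with two treatment arms and a follow-up of two years". Under Efficacy variables, secondary variable (b) begins "Rate of acute clinical rejection, confirmed by biopsy". It serves the third secondary objective, which compares immunological dysfunction between the arms.

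The kidney graft biopsy text under secondary variable (f) says who reads what:

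- **Local reading.** "Biopsies done for clinical indication and those done prior to randomization were evaluated locally at each participating center". Its purpose was to guide treatment: "The local pathologist interpreted the biopsy for the presence of clinical or subclinical rejection, borderline lesions", as well as chronic progression.
- **Central reading.** "The biopsies done and the pre-randomization and final visits were also sent to the pathologist". The central pathologist used the same Banff'09 criteria. A later sentence in the same paragraph says, without naming any visit, that biopsies were processed at the centers and sent on to the central pathologist.
- **Use of the central reading.** "The interpretation of the central pathologist was used mainly to analyze the progression of the chronic graft nephropathy". The only score defined from it is a sum of five chronic categories.
- **C4d.** It is not in the list of local stains. "For the measurement of C4d an unstained slide was sent to the reference center", and the biopsies concerned are not specified.

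Neither the protocol text nor the Statistical analysis plan says whether any reader knew the arm, which reading defines rejection, or how a local/central disagreement is settled.

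**The concern.** Outcome (b) depends on a judgement at the microscope, including the line between borderline change and rejection. In an open-label trial, a local pathologist reading a biopsy to guide treatment may learn from the request form or the clinical team that steroids were stopped. If that knowledge shifts borderline calls in one arm, the rejection difference is distorted. A masked reading would remove this, but the plan describes none for the biopsies that matter here.

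The comparison carries weight. Preliminary results give 100% graft and patient survival in both arms, so rejection is one of the few graft events on which the arms can differ. It is reported next to the primary DSA conclusion. Borderline lesions did occur in this cohort, so the boundary is not hypothetical.

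**Working it through.** **1. Which readings can be biased by arm.**

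| Biopsy | Reader named | Can knowledge of arm matter? |
|---|---|---|
| Month 3, before randomization | Local and central | No. Allocation followed the month 3 histology. |
| Indication biopsy after randomization | Local; central unclear | Yes. This is the source of outcome (b). |
| Final protocol biopsy | Central | Possible, since masking is not stated, but it is not the source of clinical rejection. |

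The exposure is therefore confined to post-randomization indication biopsies. DSA was measured in one central laboratory by a numerical threshold and is outside this point.

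**2. Reproducing the printed rates.** Inputs: 52 patients randomized to Group A and 53 to Group B (Preliminary results); rejection in 7.14% and 11.54% (section on DSA and acute rejection). Counts, denominators and p value are not given.

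- Over 52, Group A: 3/52 = 5.77%, 4/52 = 7.69%. Neither is 7.14%.
- Over 53, Group B: 6/53 = 11.32%, 7/53 = 13.21%. Neither is 11.54%.

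So neither rate is a whole count over its own randomized arm. With denominators up to the arm size, 7.14% fits 1/14, 2/28 or 3/42, and 11.54% fits 3/26 or 6/52. I take the largest fits, 3/42 and 6/52, as an assumption. They give nine events.

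- Risk ratio (RR): (6/52) / (3/42) = 0.1154 / 0.0714 = 1.62.
- Difference: 11.54 − 7.14 = 4.40 percentage points, 95% CI (Newcombe) about −9.0 to 16.8.
- Two-sided Fisher p = 0.73.

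The reported lack of significance is reproduced for every fitting pair: p lies between 0.66 and 1.0.

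**3. Effect of changed readings in Group B (Group A held at 3/42).**

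| Group B events | Rate | Risk ratio | Difference (points) | Fisher p |
|---|---|---|---|---|
| 6/52 | 11.54% | 1.62 | 4.40 | 0.73 |
| 5/52 | 9.62% | 1.35 | 2.47 | 0.73 |
| 4/52 | 7.69% | 1.08 | 0.55 | 1.0 |
| 3/52 | 5.77% | 0.81 | −1.37 | 1.0 |

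Two fewer positive readings leave a small excess. Three fewer turn it round.

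**4. Range over other counts.**

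- If Group B were 3/26, one fewer reading is enough: 2/26 = 7.69%, RR 1.08.
- With the nearest counts on the randomized denominators (4/52 and 6/53, RR 1.47, p = 0.74), two fewer readings give 4/53 = 7.55% against 7.69%, RR 0.98.

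**5. Could readings create significance?** From 3/42 and 6/52, and taking two-sided 0.05 as the level (the plan states none), p falls below it only with six more Group B events (12/52, p = 0.048; 11/52 gives p = 0.081) or with all three Group A events removed (0/42, p = 0.031).

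**The case against.** The case for leaving this alone is substantial.

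- **A reader might infer that the local pathologists were unmasked.** The documents do not say so. Open-label describes patients and treating staff, and the pathologists' knowledge of arm is neither stated nor denied. The supportable statement is that masking is not stated.
- **A reader might infer that the centers had no common standard.** They did: Banff'09 is specified for all biopsies. Only its application by one masked reader, or a deciding rule, is missing.
- **A reader might infer that indication biopsies were never read centrally.** The unqualified sentence on sending biopsies to the central pathologist may include them, the C4d sentence is equally unqualified, and a main use for chronic lesions does not exclude acute ones. This stands as far as it goes, but even if every slide was sent, nothing makes the central reading decide outcome (b).
- **A reader might treat rejection as the main safety outcome.** The plan lists it as a secondary efficacy variable, and its safety section concerns serious adverse events.
- **The conclusion would not move.** If rejection was over-called in Group B, correction brings the arms closer and leaves the result non-significant. This is right about the test. The size and direction of the difference are what depend on a few readings.
- **A masked re-reading is an incomplete cure.** Biopsy on suspicion is ordered by clinicians who know the arm, although the creatinine and proteinuria triggers are more objective. The central pathologist's hospital recruited 159 of 230 patients (69.1%), so local and central readings may not be independent there. Both limits stand.
- **Redefining the outcome now would be post hoc.** This also stands, and it determines the form of the fix.

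**Conclusion.** The point holds in a limited form. The plan leaves the rejection comparison open to reader bias because post-randomization indication biopsies are assigned to local reading in an open-label trial, with no stated masking, no clear central reading and no rule on which reading counts. Bias is possible; the documents do not show that it occurred, and they give no rate of local/central disagreement.

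On the assumed 3/42 and 6/52, the estimated difference depends on two or three readings in one arm. The non-significant finding does not. It would be wrong to say that two readings abolish the difference, since a risk ratio of 1.08 remains on those counts. The counts are inferred from rounded percentages, and 42 would leave ten of the 52 Group A patients unaccounted for, so these sizes are illustrative until the sponsor gives the real ones. A cheap improvement to a secondary outcome is warranted.

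**What to change.** 1. State who read the indication biopsies, whether arm was concealed, and whether these slides went to the central pathologist.
2. Keep local reading for treatment. Have the existing central pathologist read the post-randomization indication slides by Banff'09, with arm, center and visit removed from the labels.
3. In a plan fixed before results are known, let this masked reading define outcome (b), with the local reading as the sensitivity analysis. Here results are already reported, so keep the local result and show the masked central reading beside it as the sensitivity analysis.
4. Report local/central agreement, separately for the central pathologist's own hospital and the other four centers, because the readings may overlap at the former.
5. Give the counts and denominators behind 7.14% and 11.54%, and say why they are not 52 and 53.

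The cost is shipping, some delay, and reading a small number of slide sets: about nine rejections on the assumed counts, plus the other indication biopsies. No new biopsy or reader is needed, provided the slides still exist, which the documents do not say. The fix cannot remove bias from open-label decisions to biopsy, and the report should say so.

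### The SAP gives histology only unadjusted tests and does not say how the centrally read month-3 chronic-lesion sum enters the comparison of the arms

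*Combined protocol and SAP*

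**What the plan says.** Item 1 under Secondary objectives is "To determine the course of the histological findings in the two treatment groups". Under Efficacy variables, secondary variable f is worded as "Appearance of acute or chronic pathological lesions of the graft using" a kidney graft biopsy. Protocol biopsies are taken at month 3, before randomisation, and at the end of follow-up. Both are meant for central reading: "The biopsies done and the pre-randomization and final visits were also sent to the pathologist". That central reading "was used mainly to analyze the progression of the chronic graft nephropathy".

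The score is then defined: "For each patient, the sum of the classification of the chronic lesion was obtained from the 5 histological categories" (cg, ci, ct, cv and mm). The definition names no visit, no change from month 3 and no baseline term. The list of confounding variables that follows begins "Donor and recipient age, HLA compatibility and PRA, delayed graft function, BMI, CMV infection, concomitant treatment" and does not include month-3 histology.

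The Statistical Analysis Plan sends categorical variables to chi-square or Fisher tests and quantitative data to Student t or Mann-Whitney tests. The one adjusted longitudinal method is described thus: "Changes over time in the DSA and lymphocyte subsets in the two study groups were analyzed using a general linear model", for repeated measures and with confounder adjustment. Histology is not named there. The linear regression that closes the plan concerns factors associated with de novo DSA.

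**The concern.** The objective is about evolution over time, the central reading is there to show progression, and the trial collects the pair of readings needed. The SAP never joins the two readings in an analysis. Followed literally, it allows a t or Mann-Whitney test on the final sum alone. That test ignores a baseline measurement likely to be related to the outcome, because the final sum includes lesions that came with the donor kidney or arose in the first three months, when both arms had the same treatment schedule.

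Two things are at stake. One is precision in a trial that randomised only 105 patients. The other is clarity: without a stated outcome and model, the final sum, a change score, an adjusted final sum or a subgroup contrast could each be presented as the answer to objective 1. The histology section of the Preliminary results gives month-3 to month-24 increases and subgroup comparisons, but no comparison of the chronic sum between Group A and Group B.

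**Working it through.** The documents give no SD, effect size, power or significance level for histology, so there is no planned figure to reproduce.

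**Inputs**
- 52 patients in Group A and 53 in Group B (Preliminary results).
- 1:1 randomisation, done after the month-3 histology is known (Selection procedure and coding).
- Assumed: equal SD of the sum at both visits; correlation r between month-3 and final sums of 0.3, 0.5 or 0.7; paired readings in all 105 patients. Results are in SD units because no SD is given.

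**Step 1. Is the unadjusted comparison biased?** Let X be the month-3 sum and Y the final sum. X is fixed before allocation, so its expected value is the same in both arms. The expected arm difference in Y therefore equals the expected arm difference in Y − X. The final sum, the change score and linear ANCOVA all estimate the same mean effect. They differ in precision.

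**Step 2. How large can a chance month-3 imbalance be?** SE = √(1/52 + 1/53) = √0.0381 = 0.195 SD. The 95% range is ±1.96 × 0.195 = ±0.38 SD.

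**Step 3. How much passes into an unadjusted final comparison?** Carry-over is r × imbalance, shown below for an imbalance at the edge of that range.

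**Step 4. What does adjustment gain?** Relative to the unadjusted final sum, the standard error is multiplied by √(1 − r²) for ANCOVA and by √(2(1 − r)) for a change score.

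| Assumed r | Carry-over of 0.38 SD | SE factor, ANCOVA | SE factor, change score |
|---|---|---|---|
| 0.3 | 0.11 SD | √0.91 = 0.954 | √1.4 = 1.183 |
| 0.5 | 0.19 SD | √0.75 = 0.866 | √1.0 = 1.000 |
| 0.7 | 0.27 SD | √0.51 = 0.714 | √0.6 = 0.775 |

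**Step 5. In terms of detectable difference.** With an assumed two-sided 5% level and 80% power, the smallest detectable difference for the unadjusted final sum is (1.960 + 0.842) × 0.195 = 0.55 SD. Multiplied by the factors above, it becomes 0.52, 0.47 or 0.39 SD for ANCOVA and 0.65, 0.55 or 0.42 SD for a change score. A change score is thus worse than ignoring month 3 when r is below 0.5. ANCOVA is more precise than either at all three values.

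**Step 6. If fewer pairs exist.** The number of paired central readings is not reported. With 19 per arm, taken only to show the direction, the range in step 2 widens to ±1.96 × √(2/19) = ±0.64 SD, and the carry-over to 0.19, 0.32 or 0.45 SD.

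**The case against.** The strongest reply is that the plan is silent here, not wrong. A reader might infer that the month-3 central reading goes unused. The documents do not say so: the biopsy is sent for central reading, progression cannot be judged from one reading, the sum has no stated visit, and the Preliminary results report increases from month 3 to month 24 (without saying whose reading was used). The t or Mann-Whitney test could also be applied to a change in the sum. All of this stands, so the point is confined to what the plan leaves unspecified.

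A reader might also infer that lesions present at randomisation would be counted as a treatment effect, so that the analysis has the wrong target. Step 1 rules that out as a systematic error. A valid unadjusted test also allows for chance baseline imbalance in its standard error and keeps its type I error. The carry-over figures show how far a single result may be shifted by month-3 imbalance, which is another view of the same imprecision.

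Finally, the absence of an arm comparison of the chronic sum in the Preliminary results is a matter of reporting. It does not show what was planned.

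What survives is that no sentence of the SAP says how the month-3 sum enters the randomised comparison, the tests it does name are unadjusted, and month-3 histology is missing from the confounder list. A simple and more precise method is available from data the trial already collects.

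**Conclusion.** The concern holds as a gap in specification with a cost in precision. Applied to the final sum, the stated tests are unbiased on average but have a standard error larger than necessary: adjustment would reduce it by about 5%, 13% or 29% for r of 0.3, 0.5 or 0.7. They also leave the estimate exposed to chance month-3 imbalance within about ±0.38 SD, worth up to 0.11, 0.19 or 0.27 SD in the final comparison. These sizes rest on assumed correlations, equal SDs and complete pairs. The documents supply none of these, and fewer pairs would widen the imbalance range.

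The documents do not support the conclusions that month 3 was ignored, that the comparison is biased, or that objective 1 cannot be answered. Because this is a secondary objective and the scores should already exist, the change is worth making and cheap.

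**What to change.** Add to the SAP that the randomised histology comparison is the final central chronic-lesion sum, Group A versus Group B as randomised, adjusted for the month-3 central sum. Use ANCOVA, or a proportional-odds model if the sum is treated as ordinal. Report the estimate with its confidence interval ahead of the subgroup results. In the same place, state the visit for the final sum: the Efficacy variables section counts the final biopsy from randomisation, the Preliminary results count 24 months from transplant, and the two must be reconciled.

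The cost is a short SAP addition and a rerun on scores already read. As preliminary results exist, the addition should be dated and described as made after they were known.

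The drawback is missing readings. A month-3 biopsy should exist for nearly everyone, because its findings are needed before randomisation, although a few may be unreadable centrally. The likelier loss is the final biopsy, which occurs after randomisation and may differ by arm, so an analysis limited to complete pairs is no longer fully protected by randomisation. Report the number missing by arm at each visit, and add a sensitivity analysis for missing final biopsies, for example multiple imputation from arm, month-3 sum and renal function, with shifts to test departures from missing at random.
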